2.1 Data analysis general information

The data will be analyzed by Novartis personnel and/or designated CRO(s) using the most updated version of SAS, R and JAGS. PK parameters will be calculated using non-compartmental methods available in most updated version of Phoenix WinNonlin.

Data from participating centers in this study protocol will be combined, so that an adequate number of patients will be available for analysis. No center effect will be assessed. The data will be summarized with respect to demographic and baseline characteristics, efficacy observations and measurements, safety observations and measurements, and all relevant pharmacokinetic (PK) and pharmacodynamics (PD) measurements using descriptive statistics (n, mean, standard deviation, median, minimum, and maximum) for quantitative data and contingency tables (frequencies and percentages) for qualitative data.

Data will be summarized and listed by study arms or by study treatment groups. Details are specified in each of the subsections.

Study arms refer to

- PDR001
- Chemotherapy

Study treatment groups refer to

- PDR001
- Chemotherapy
- Crossover

Crossover treatment group consists of the patients in the chemotherapy arm who crossover to PDR001 and treated with PDR001 after progression to chemotherapy. The clinical data collected before the crossover will be summarized in the chemotherapy treatment group; the clinical data collected after the crossover will be summarized or listed as appropriate in crossover treatment group.

2.1.1 General definitions

Study drug and study treatment

Study drug refers to PDR001. Study treatment refers to both PDR001 and Chemotherapy. Chemotherapy used in control arm may differ across centers.

Date of first/last administration of study drug and study treatment

The date of first (last) administration of study treatment is derived as the first (last) date when a non-zero dose of study treatment was administered and recorded on the Dosage Administration Record (DAR) eCRF. For the sake of simplicity, the date of first (last) administration of study treatment will also be referred as start (last) date of study treatment.

Study day

For PDR001 and Chemotherapy treatment group:

The study day for safety assessments/events will be calculated using the start date of study treatment as reference. The study day for efficacy assessments/events will be calculated using the date of randomization as reference.

For safety assessments/events occurring on or after the start date of study treatment, study day will be calculated as:

$$\text{Study day (days)} = \text{Event date} - \text{Start date of study treatment} + 1$$

Therefore, the first day of study treatment is study day 1.

For safety assessment/events occurring prior to the start of the study treatment, study day will be negative and will be calculated as:

$$\text{Study day (days)} = \text{Event date} - \text{Start date of study treatment}$$

For efficacy assessments/events occurring on or after randomization, study day will be calculated as:

$$\text{Study day (days)} = \text{Event date} - \text{Date of randomization} + 1$$

For efficacy assessment/events occurring prior to randomization, study day will be negative and will be calculated as:

$$\text{Study day (days)} = \text{Event date} - \text{Date of randomization}$$

Study day will be displayed in the data listings.

For Crossover treatment group:

The study day for safety and efficacy assessments/events will be calculated using the start date of PDR001 treatment as reference.

For assessments/events occurring on or after the start date of PDR001 treatment, study day will be calculated as:

Study day (days) = Event date – Start date of PDR001 treatment + 1

Therefore, the first day of PDR001 treatment is study day 1.

For assessment/events occurring prior to the start of the PDR001 treatment, study day will be negative and will be calculated as:

Study day (days) = Event date – Start date of PDR001 treatment

On-treatment assessment/event

For PDR001 arm, an on-treatment assessment/event is defined as any assessment/event obtained in the time interval from the start date of study treatment until the minimum date of (last date of study treatment + 30 days).

For crossover treatment group, an on-treatment assessment/event is defined as any assessment/event obtained in the time interval from the start date of PDR001 treatment until the minimum date of (last date of study treatment + 30 days).

For chemotherapy arm, an on-treatment assessment/event is defined as any assessment/event obtained in the time interval from the start date of study treatment until the minimum date of (the last date of study treatment + 30 days inclusive, start of crossover PDR treatment if crossed over).

2.2 Analysis sets

The number (%) of patients in each of the defined analysis set will be summarized using the FAS.

Full Analysis Set

The Full Analysis Set (FAS) comprises all patients to whom study treatment has been assigned by randomization. According to the intent to treat principle, patients will be analyzed according to the treatment (and strata) they have been assigned to during the randomization procedure. The FAS will be the primary population for all efficacy related data analyses.

Safety Set

The Safety Set includes all patients who received at least one dose of study medication and have at least one valid post-screening/post-baseline safety assessment. Patients will be analyzed according to the study treatment (regimen) they received.

The statement that a patient had no AEs (on the AE eCRF) constitutes a valid safety assessment. Patients will be classified according to treatment received, where treatment received is defined as:

- The treatment assigned if it was received at least once, or
- If the assigned treatment was never received, then the first treatment received when starting therapy with study treatment will be used for classification

The safety set will be the primary population for all safety related endpoints.

Per-protocol Set

The Per Protocol Set (PPS) consists of a subset of FAS patients who meet the following criteria:

- Treatment according to the randomization scheme (see [CPDR01X2201-Protocol-Section 6](#)).
- Presence of at least one measurable lesion at screening/baseline according to RECIST v1.1 as per [CPDR01X2201-Protocol-Appendix 1](#).
- At least 2 post-screening/post-baseline tumor assessments (unless disease progression is observed before that time).
- Have not been previously treated with PD-1- or PD-L1-directed therapy or any therapeutic cancer vaccine.

Patients will be classified according to treatment received.

In the final CRS no sensitivity analysis with PPS will be conducted.

Pharmacokinetic analysis set

The pharmacokinetic analysis set (PAS) consists of all patients who have at least one dose of PDR001 and have at least one evaluable concentration measurement of PDR001. The PAS will be used for all PK analyses.

Note: Patients may be removed from the estimation of certain PK parameters on an individual basis depending on the number of available blood samples. These patients will be identified at the time of analysis along with their reason for removal.

Immunogenicity (IG) analysis set

The Immunogenicity prevalence set includes all subjects in the Safety analysis set with a determinant baseline IG sample **or** at least one determinant post-baseline IG sample.

The Immunogenicity incidence set includes all subjects in the Immunogenicity prevalence set with a determinant baseline IG sample **and** at least one determinant post-baseline IG sample.

See Section [2.9.2](#) for the definition of determinant.

2.2.1 Analysis set exclusion

Patients will be excluded from the analysis sets based on the protocol deviations and specific non-protocol deviations entered in the database. All protocol deviations and non-protocol

deviations leading to exclusion from specific analysis sets will be identified before database lock. Details in Table 2-1.

Table 2-1 Protocol deviation and non-protocol deviation leading to exclusion from analysis set definitions

Analysis set	PDs leading to exclusion (ID)	Non-PDs leading to exclusion
FAS Safety set	No written inform consent (INCL01).	No administration of study drug. No valid post-baseline safety assessment.
PPS	No written inform consent (INCL01). Receive study treatment not according to the randomization scheme (i.e., randomize to PDR but receive Chemotherapy, vice versa) (TRT01, TRT02) Patient has no measurable lesion as determined by RECIST 1.1 at baseline (INCL09) Have been previously treated with PD-1- or PD-L1-directed therapy or any therapeutic cancer vaccine. (INCL14)	No administration of study drug. Less than 2 post-screening/post-baseline tumor assessments (unless disease progression is observed before that time).
PAS	No written inform consent (INCL01).	No administration of study drug. No evaluable PK data.
Immunogenicity prevalence set	No written inform consent (INCL01).	No administration of study drug. No determinant IG sample at both baseline and post-baseline
Immunogenicity incidence set	No written inform consent (INCL01).	No administration of study drug No determinant IG sample at baseline or post-baseline or both

2.2.2 Withdrawal of Informed Consent

Any data collected in the clinical database after a subject withdraws informed consent from all further participation in the trial, will not be included in the analysis. The date on which a patient withdraws full consent is recorded in the eCRF.

Additional data for which there is a separate informed consent, e.g. PK, biomarker etc., collected in the clinical database without having obtained that consent will not be included in the analysis. These data will be excluded by the presence of the appropriate protocol deviation criterion.

2.2.3 Subgroup of interest

No subgroup analysis will be conducted in the final CSR as the primary efficacy analysis reported in the interim CSR was not statistically significant.

2.3 Patient disposition, demographics and other baseline characteristics

Summaries and listings described in this section will be done by study arms based on the FAS.

2.3.1 Patient disposition

The FAS will be used for the patient disposition summary tables and listings. The following will be tabulated:

- Number (%) of patients who are still on-treatment (based on non-completion of the 'End of Treatment' page),
- Number (%) of patients who discontinued treatment (based on completion of the 'End of Treatment' page with discontinuation date and reason entered),
- Primary reasons for study treatment discontinuation (based on discontinuation reason entered in the 'End of Treatment' page),
- Number (%) of patients who discontinued from study (based on completion of the 'End of Post Treatment Phase Disposition' page with discontinuation date and reason entered),
- Primary reasons for study evaluation completion (based on discontinuation reason entered in the 'End of Post Treatment Phase Disposition' page).

2.3.2 Basic demographic and background data

Demographic data including age, sex, race, ethnicity, height, and baseline weight and ECOG(WHO) performance status will be listed and summarized. In addition, body mass index (BMI) and child bearing potential will be listed, and age (18-<65, 65-<85, ≥85 years) categories will be summarized.

BMI is calculated using the following formulas:

- $BMI [kg/m^2] = weight[kg] / (height[m]**2)$

2.3.3 Medical History

Medical history and current (ongoing) medical conditions will not be reported in the final CSR.

2.3.4 Prior antineoplastic therapy

Prior anti-neoplastic therapy will not be reported in the final CSR.

2.3.5 Diagnosis and extent of cancer

Diagnosis and extent of cancer (disease history) will not be reported in the final CSR.

2.4 Protocol deviations

Summaries and listings described in this section will be done by study arms based on the FAS.

The number (%) of patients with any protocol deviation will be tabulated by the deviation category (selection criteria not met; study treatment deviation; not discontinued after meeting

withdrawal criteria; use of prohibited concomitant medication; other deviation). The full list of protocol deviations are documented in the Study Specification Document (SSD). COVID-19 specific protocol deviations will be listed. Details about COVID-19 impact are provided in [Section 4.1](#).

2.5 Treatments (study treatment, rescue medication, other concomitant therapies, compliance)

Summaries and listings described in this section will be done by study treatment groups based on the Safety set. Exceptions are specified in each subsection.

2.5.1 Study treatment

Study treatment refers to:

- PDR001
- Chemotherapy: as per investigator's choice

Below summaries will be done for PDR001 treatment group. For chemotherapy, Duration of exposure (days) and Duration of dose interruptions (days) will be summarized, dosage administration records will be listed by patient and by each chemotherapy per investigator's choice. For patients in Chemotherapy arm who crossover to PDR001 after progression to chemotherapy, below summaries will be done as well for PDR001 treatment if there are more than 10 crossover patients.

Duration of exposure to PDR001 = (last date of exposure to PDR001) – (date of first administration of PDR001) + 1.

The last date of exposure to PDR001 is defined as: minimum date of (date of last administration of a non-zero dose of the PDR001 + 27 days, data cutoff date, death date);

Duration of exposure to Chemotherapy = (last date of exposure to Chemotherapy) – (date of first administration of Chemotherapy) + 1

The last date of exposure to Chemotherapy is defined in [Table 2-2](#).

Table 2-2 Definition of last date of exposure to chemotherapy

Regimen	Definition of last date of exposure*
Daily administration of the study treatment, i.e., BID, QD and EVERY OTHER DAY	Date of last administration of a non-zero dose
study treatment with a cyclic administration: - WEEKLY (EVERY 7 DAYS) - 1 WEEK ON 3 WEEKS OFF - 21 DAYS ON 7 DAYS OFF - 2 WEEKS ON 1 WEEK OFF - 2 WEEKS ON 2 WEEKS OFF	The planned end date of the last cycle in which the last non-zero dose of the study treatment was administered: the date of first administration of study treatment in the last cycle + cycle length - 1 i.e., for 1 WEEK ON 3 WEEKS OFF, the cycle length is 28 days, last date of exposure = the date of first

- 2 WEEKS ON 3 WEEKS OFF - EVERY 2 WEEKS - EVERY 3 WEEKS - EVERY 4 WEEKS	administration of study treatment in the last cycle + 27 days; For EVERY 2 WEEKS, the cycle length is 14 days, last date of exposure = the date of first administration of study treatment in the last cycle + 13 days;
---	--

* If the derived last date of exposure goes beyond the data cutoff date, death date, then it should be truncated to the date of the minimum of (data cutoff date, death date).

Definitions of cumulative dose, actual dose intensity (DI), planned dose intensity (PDI), relative dose intensity (RDI), percentage of cycles dosed, percentage of cycles at the prescribed dose was received, as well as intermediate calculations, are as follows:

- Duration of dose interruptions (days): Sum of all dose delays. See definition of dose delay/interruption below.
- Cumulative dose (mg): sum of all doses of study drug taken by a patient
- Cumulative prescribed dose (mg): sum of all doses of study drug that was intended to have been taken during the treated period by a patient
- DI (mg/cycle): cumulative dose (mg)/number of doses scheduled per protocol during treatment period
- PDI (mg/cycle): cumulative prescribed dose (mg)/number of doses scheduled per protocol during treatment period
- RDI (%): $100 \times \text{DI (mg/cycle)} / \text{PDI (mg/cycle)}$

The duration of exposure to study treatment (including categories: ≤ 4 weeks, $4 < \leq 12$ weeks, $12 < \leq 16$ weeks, $16 < \leq 24$ weeks and > 24 weeks) will be summarized. In addition, the cumulative dose, DI, and RDI (including categories: < 0.5 , $\geq 0.5 < 0.75$, $\geq 0.75 < 0.9$, $\geq 0.9 < 1.1$, ≥ 1.1) will be summarized. The number (%) of patients who have dose interruptions and dose reductions, and the corresponding reasons, will be provided. The number of dose interruptions and dose reductions per patient and the duration of interruptions and dose reductions will be summarized.

All doses of the study treatment along with reasons for any dose change will be listed.

Dose interruption: 'Dose interrupted' field from the Dosage Administration CRF pages (DAR) will be used to determine the dose interruptions. For patients in Chemotherapy arm taking doublet or triplet chemotherapies, if 'Dose interrupted' field is ticked for all of the combo/triple components on the same day, then only count the dose interruption once.

2.5.2 Concomitant therapies

Concomitant therapies will not be reported in the final CSR.

2.5.3 Compliance

Compliance to the protocol will be assessed by the number and percentage of patients with protocol deviations. Details are provided in [Section 2.4](#).

Compliance to the study treatment PDR001 will be assessed by the percentage of patients who took a predefined percentage (RDI categories: <0.5, 0.5-<0.75, 0.75- <0.9, 0.9-<1.1, ≥1.1) of the number of prescribed doses of study treatment. Details are provided in Section 2.5.1.

2.6 Analysis of the primary objective

2.6.1 Primary endpoint

The primary efficacy endpoint is progression-free survival (PFS) based on central review of tumor scan, as defined per RECIST v1.1 ([CPDR01X2201-Protocol-Appendix 1](#)).

PFS is the time from the date of randomization to the date of event defined as the first documented confirmed progression or death due to any cause. If a patient has not had an event, progression-free survival is censored at the date of last adequate tumor assessment.

2.6.2 Statistical hypothesis, model, and method of analysis

Patients are randomized in 2:1 ratio into either PDR001 arm or control arm. The primary efficacy endpoint, PFS as determined based on the central tumor assessment per RECIST v1.1, will be analyzed by study arm.

Kaplan-Meier plots will be provided in order to present PFS graphical outputs for the PDR001 and the control arm. KM estimates of the median and PFS rates at 2, 4, 6, 8 and 12 months will be given along with 95% confidence intervals. The FAS will be used for the primary analysis. In addition to the primary PFS analysis by study arm the KM estimates will be analyzed by PD-L1 and CD8 expression.

2.7 Analysis of the secondary efficacy variables

Evaluation of anti-tumor activity will be based on central review of overall lesion response according to RECIST v1.1 (see [CPDR01X2201-Protocol-Appendix 1](#)) and irRC ([CPDR01X2201-Protocol-Appendix 2](#)). The variables used to evaluate anti-tumor activity are OS, ORR, BOR, DOR, TTP as per RECIST v1.1 and irPFS as per irRC. Summaries and listings described in this section will be done by study arms based on the FAS.

Individual lesion measurements, overall lesion response, OS, DOR, and irPFS will be listed by patient. OS, ORR, BOR, DOR, TTP and irPFS will be summarized as per specification in [Table 2-3](#). A waterfall plot of best percentage change from baseline in sum of longest diameters of target lesions per RECIST 1.1 and total measured tumor burden (TMTB) per irRC ([CPDR01X2201-Protocol-Appendix 2](#)) will be presented for each study treatment group.

Table 2-3 Analysis of the secondary efficacy variables

Endpoint	Definition	Analysis
----------	------------	----------

OS	Time from the date of randomization to date of death due to any cause. If a patient is not known to have died, survival will be censored at the date of last known date patient alive.	A Kaplan-Meier plot for OS will be presented. Median OS (in months) with corresponding 95% CI, 25th and 75th percentiles (Brookmeyer and Crowley 1982, Klein and Moeschberger 1997) and Kaplan-Meier estimated probabilities (OS rate) with corresponding 95% CIs (Greenwood's formula, Kalbfleisch and Prentice 1980) at several time points (6, 12, 18 and 24 months) will be presented. The number (%) of deaths and patients censored will also be summarized.
irPFS (per irRC)	Time from the date of randomization to the date of the first documented disease progression (irPD) (CPDR01X2201-Protocol-Appendix 2), or death due to any cause.	Median irPFS (in months) with corresponding 95% CI, 25th and 75th percentiles (Brookmeyer and Crowley 1982, Klein and Moeschberger 1997) and Kaplan-Meier estimated probabilities (irPFS rate) with corresponding 95% CIs (Greenwood's formula, Kalbfleisch and Prentice 1980) at several time points (2, 4, 6, 8 and 12 months) will be presented. The number (%) of progressions, deaths and patients censored will also be summarized. The analysis of irPFS will be done for PDR001 arm and crossover patients if there are more than 10 crossover patients.
TTP (per RECIST 1.1)	Time from date of randomization to the date of event defined as the first documented progression or death due to underlying cancer. If a patient has not had an event, time to progression is censored at the date of last adequate tumor assessment.	Median TTP (in months) with corresponding 95% CI, 25th and 75th percentiles (Brookmeyer and Crowley 1982, Klein and Moeschberger 1997) and Kaplan-Meier estimated probabilities (TTP rate) with corresponding 95% CIs (Greenwood's formula, Kalbfleisch and Prentice 1980) at several time points (2, 4, 6, 8 and 12 months) will be presented. The number (%) of progressions, deaths and patients censored will also be summarized.

BOR (per RECIST 1.1)	The best overall response (BOR) is the best response recorded from the start of the treatment until disease progression/recurrence.	BOR will be summarized as observed proportion in each category, and corresponding 95% confidence intervals (CIs) based on the exact binomial distribution will be presented. Tumor volume best change from baseline of solid tumors will be presented graphically (waterfall graphs). Tumor assessments performed more than 30 days after the last study treatment (and before any new anti-neoplastic therapy) have to be considered in derivation of the BOR.
ORR (per RECIST 1.1)	Proportion of patients with a best overall response of confirmed CR or confirmed PR.	ORR and corresponding 95% confidence intervals (CIs) based on the exact binomial distribution will be presented.
DOR (per RECIST 1.1)	Time from the date of first documented response (confirmed CR or confirmed PR) to the date of the first documented disease progression or death due to underlying cancer.	Summaries of DOR will be provided if at least 10 patients responded to study treatment. Present DOR rate at 6, 10, 12, 18, 24 months.

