Moreover, Kaplan-Meier plots will be provided in order to present PFS graphical outputs for the PDR001 and the control arm. KM estimates of the median and PFS rates at 2, 4, 6, 8, 10 and 12 months will be given along with 95% confidence intervals. The FAS will be used for the primary analysis. A stratified Cox regression model will also be used to estimate the HR of PFS as supplementary analysis,

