#### **10.5.2 Other secondary efficacy objectives**

Efficacy endpoints ORR, BOR and TTP will be also assessed. irPFS will be derived using irRC ([Appendix 2](#)) based on central assessments. An immune related progression disease (irPD) is confirmed by 2 repeated scans at least 4 weeks apart from date of first documented irPD, and the date of 1st scan is defined as the date of irPD.

Individual lesion measurements, overall lesion response, duration of response (DOR), BOR, irPFS and OS will be listed by patient. BOR and ORR will be summarized by treatment arm with accompanying 95% confidence intervals. OS and DOR will be presented descriptively using Kaplan Meier plots. Median OS and DOR will be estimated along with 95% confidence

intervals. The OS rates along with 95% CIs will be provided at 6, 12, 18 and 24 months for each treatment arm using the Kaplan Meier distribution. A stratified Cox regression model will be used to estimate the HR of PDR001 arm vs. the control arm in OS and irPFS, respectively, along with 95% CI for HR.

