1.2 Study objectives and endpoints

Objectives and related endpoints are described in [Table 1-1](#) below.

Table 1-1 Objectives and related endpoints

Objective	Endpoint	Analysis
Primary		
To assess the efficacy of PDR001 versus investigator's choice of chemotherapy in patients with moderately differentiated/undifferentiated locally advanced recurrent or metastatic NPC who progressed on or after first-line therapy	Progression free survival (PFS) as per RECIST v1.1 using central assessment	Section 2.6
Secondary		
To evaluate the anti-tumor activity of PDR001 versus investigator's choice of chemotherapy in patients with moderately differentiated/undifferentiated locally advanced recurrent or metastatic NPC who progressed on or after first-line therapy	Overall survival (OS), overall response rate (ORR), duration of response (DOR), time to progression (TTP) and immune related progression free survival (irPFS) as per irRC using central assessment	Section 2.7
To characterize the safety and tolerability of PDR001	Safety: Incidence and severity of adverse events (AEs) and serious adverse events (SAEs), including changes in laboratory parameters, vital signs and electrocardiograms (ECGs)	Section 2.8

Objective	Endpoint	Analysis
To characterize the pharmacokinetic profile of PDR001 (patients in PDR001 arm)	Serum PK parameters (e.g. AUC, Cmax, Tmax, half-life); Serum concentration vs. time profiles	Section 2.9
To assess emergence of anti-PDR001 antibodies following one or more intravenous (i.v.) infusions of PDR001 (patients in PDR001 arm)	Presence and/or concentration of anti-PDR001 antibodies	Section 2.10
To assess potential predictive markers of efficacy of PDR001 in tumor sample (patients in PDR001 arm)	Assess potential associations between expression of PD-L1, CD8, Foxp3 and other immunological markers such as Lymphocyte activation gene-3 (LAG-3), T-cell immunoglobulin domain and mucin domain-3 (TIM-3), with anti-tumor activity	Section 2.10
To assess the pharmacodynamic effect of PDR001 in tumor sample (patients in PDR001 arm)	TIL counts and expression of immune-related genes (RNA/protein in tumor sample)	Section 2.10
To assess the pharmacodynamic effect of PDR001 in peripheral blood (patients in PDR001 arm)	Assess peripheral, soluble ligands and cytokine levels (including but not limited to IFN- γ , TNF- α , IL-6)	Section 2.10

2 Statistical Methods

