4.1 Planned analyses due to COVID-19

The COVID-19 pandemic had minimal impact on this study because at the start of the pandemic, the vast majority of subjects had discontinued the study treatment and completed the safety follow-up phase. COVID-19 specific protocol deviations will be listed.

5 Appendix

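### The SAP for the final CSR drops the protocol's stratified Cox hazard ratio for overall survival without declaring it, leaving by-arm summaries and no between-arm estimate.

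*SAP*

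**What the plan says.** Protocol 10.5.2 first describes OS by Kaplan-Meier curves, medians and rates at 6, 12, 18 and 24 months. It then adds a comparative analysis: "A stratified Cox regression model will be used to estimate the HR of PDR001 arm vs. the control arm in OS and irPFS", with a 95% CI for the HR. Nothing makes this conditional on the primary result or on a particular data cutoff.

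The SAP, which covers the final CSR, keeps the secondary objective comparative: "To evaluate the anti-tumor activity of PDR001 versus investigator's choice of chemotherapy". Its Table 1-1 sends that objective to SAP 2.7, which says of its contents: "Summaries and listings described in this section will be done by study arms based on the FAS". Table 2-3 then specifies OS. It starts with "A Kaplan-Meier plot for OS will be presented" and adds the median with CI, the quartiles, rates at the four time points with CIs, and the numbers of deaths and censored patients. No Cox model or HR is listed.

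Section 4 of the SAP is reserved for changes to the analyses in the protocol. Its only entry is "4.1 Planned analyses due to COVID-19".

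Other omissions are announced where they occur. For the per-protocol set: "In the final CRS no sensitivity analysis with PPS will be conducted". For subgroups, with a reason: "No subgroup analysis will be conducted in the final CSR as the primary efficacy analysis reported in the interim CSR was not statistically significant".

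**The concern.** A randomised comparison is normally summarised by an effect estimate with its uncertainty. For OS the protocol promises one and the SAP plans none, so the comparative objective has no comparative OS analysis behind it. The final CSR should hold the longest survival follow-up, which makes it the natural place for this estimate.

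The silence is a separate problem. The SAP states in 2.2.3 that the primary result was already known and not significant. A protocol-specified estimate that disappears after that point, without explanation, cannot be told apart from a choice made in the light of the data. This is a point about traceability. Nothing in the documents shows that the choice was driven by results.

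Two lesser gaps go with it. Protocol 10.4.2 says "A stratified Cox regression model will also be used to estimate the HR of PFS as supplementary analysis", and SAP 2.6.2 has no such model. For immune-related PFS (irPFS), the same sentence of protocol 10.5.2 plans an HR between arms, while SAP Table 2-3 restricts the analysis to the PDR001 arm and crossover patients. That restriction also conflicts with the by-arm statement in SAP 2.7.

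**Working it through.** **Comparison of the texts**

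| Item | Protocol | SAP for the final CSR | Declared in SAP section 4? |
|---|---|---|---|
| OS, Kaplan-Meier by arm | 10.5.2: yes | Table 2-3: yes | not needed |
| OS, stratified Cox HR with 95% CI | 10.5.2: yes | absent | no |
| irPFS, stratified Cox HR with 95% CI | 10.5.2: yes | absent; PDR001 arm and crossover only | no |
| PFS, supplementary stratified Cox HR | 10.4.2: yes | absent | no |

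In the available SAP text, a hazard ratio is mentioned only in section 3, in the sample size for PFS.

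**The plan's own figure.** The only sizing figure is 70 PFS events for 85% power at HR 0.55, one-sided alpha 0.10, 2:1 allocation. The Schoenfeld formula gives

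events = (1.2816 + 1.0364)² / [(2/3)(1/3)(ln 0.55)²] = 67.7, so 68.

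Power at 70 events is 0.859. Both agree with the plan, so the same variance formula is used below for OS.

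**Precision of the missing OS HR.** Inputs: 122 randomised, 82 of them to PDR001 (protocol, Amendment 06 study status), so 40 controls and p = 82/122 = 0.672. The documents give no death count, so d is assumed.

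SE(log HR) = 1/√[d·p·(1−p)]; 95% CI = HR multiplied or divided by exp(1.96·SE).

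| Deaths (assumed) | SE(log HR) | CI factor |
|---|---|---|
| 60 | 0.275 | 1.71 |
| 80 | 0.238 | 1.59 |
| 100 | 0.213 | 1.52 |
| 110 | 0.203 | 1.49 |

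At 80 deaths, an observed HR of 0.80 would have a 95% CI of 0.80/1.59 to 0.80×1.59, about 0.50 to 1.28.

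**Is that range of deaths plausible?** Assume exponential survival with the same median in both arms and 24 months of follow-up for each patient.

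- Without losses, P(death) = 1 − 0.5^(24/median).
- With losses, P(death observed) = h/(h+c)·[1 − exp(−24(h+c))], where h = ln 2/median and c = −ln(0.85)/12 = 0.01354 per month. This uses the plan's 15% dropout at 12 months.

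| Median OS (months) | Source | Deaths, no losses | Deaths, with losses |
|---|---|---|---|
| 7.2 | lowest in protocol Table 1-1 | 0.901×122 = 109.9 | 0.814×122 = 99.3 |
| 12 | protocol 1.1 | 0.750×122 = 91.5 | 0.664×122 = 81.0 |
| 13 | protocol 1.1 | 0.722×122 = 88.1 | 0.637×122 = 77.7 |
| 16 | highest in protocol Table 1-1 | 0.646×122 = 78.9 | 0.567×122 = 69.2 |

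The assumed counts of 60 to 110 cover this range.

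**The case against.** *The commitment may already have been met.* This SAP covers the final CSR only, and an interim CSR exists. Protocol section 10 puts selected secondary endpoints into the primary analysis, and 10.5.2 does not say which report must carry the OS HR. The plan for the interim CSR, the output shells and SAP section 2.12 are not available. This stands as a limit: one cannot say that no OS HR was ever produced. It does not close the gap, because the SAP gives no pointer to one and an earlier HR would rest on less mature data.

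*The final report is simply abbreviated.* SAP 2.6.2 also lacks the log-rank test and the Bayesian model, and several background summaries are dropped. This explains the pattern and makes a deliberate simplification likely. But those background items are announced and the OS HR is not. Appendix 1 of the protocol (14.1.4.1) requires departures from the protocol to be defined at the latest in the analysis plan.

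*Readers are not left with nothing.* By-arm OS rates with CIs are planned, and the arms are independent, so a rate difference and its SE at 6, 12, 18 or 24 months can be derived. This is right, and it would be too strong to say that only two medians can be compared. The SAP itself still plans no between-arm estimate.

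*OS has no alpha, and crossover blurs the HR.* OS carries no formal hypothesis, so omitting the HR cannot create a false positive claim. Crossover does complicate interpretation, but it affects the planned Kaplan-Meier curves equally. It calls for a label, not for omission.

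*The death counts are assumptions.* The 15% dropout was set for PFS planning, and the 12 to 13 month median refers to previously treated patients generally. Follow-up could exceed 24 months for patients enrolled early, or be shorter under the other end-of-study criteria in protocol 4.3. All of this is so. The finding does not depend on the counts, which only indicate precision.

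*irPFS in controls is hardly observable.* Immune-related progression needs confirmation at least 4 weeks later. Crossover should start within 21 days of the last scan, and the chemotherapy visit schedule lists RECIST v1.1 only, although protocol 7.2.1 names both criteria for tumour response. This is a good reason for the restriction, and section 4 should state it.

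**Conclusion.** The concern holds. The protocol requires a stratified Cox HR with 95% CI for OS, the SAP for the final CSR does not plan it, and the section for declaring changes says nothing about it. That rests on the texts alone and is certain for the SAP text available.

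The loss is a between-arm estimate of moderate precision. Under the assumed 60 to 100 deaths the 95% CI is the HR multiplied or divided by 1.71 to 1.52. An estimate of that width would probably not settle whether survival differs, but it is the summary the protocol promised, from data the SAP already analyses. The change should be made. The missing PFS HR matters less, since the primary PFS analysis is already reported. The irPFS point needs a declaration and a reconciliation, not a new analysis.

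**What to change.** - **SAP Table 2-3, OS row:** add the HR (PDR001 versus chemotherapy, FAS) with 95% CI from a Cox model stratified by disease status. Note that control-arm OS includes time after crossover to PDR001, so the HR compares the arms as randomised whatever treatment followed.
- **If the OS HR is left out on purpose:** say so in SAP section 4, give the reason, and say where the OS HR is reported.
- **SAP 2.6.2:** add the stratified Cox HR for PFS, or state that it was reported in the interim CSR.
- **SAP section 4:** declare that irPFS is no longer compared between arms, with the reason, and reconcile this with the by-arm statement in SAP 2.7.

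The cost is a few lines of SAP text and one standard model output. No new data are needed.
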